## ***F2 Interim Monitoring and Early Stopping***

The DSMB will provide oversight and ongoing monitoring of participant safety, quality of data collection, and integrity of the study on a yearly basis. The DSMB will receive a report from the study Screening Implementation and Data Coordinating Center approximately four weeks before each review date. These reports will include the major variables necessary for monitoring safety, quality of data collection, and integrity of the study and will include otherwise blinded outcome data. The DSMB will prepare a report after every meeting based on the material received from the Screening Implementation and Data Coordinating Center, which will be forwarded to the PIs to review at Study Executive Committee meetings and also forwarded to the IRB of Record by [name].

## ***F3 Analysis Plan***

To evaluate efficacy of the mHealth platform vs. usual care, in engaging participants (Aim 1) we will use hierarchical logistic regression to examine uptake (i.e., individuals beginning any sort of treatment). Outcome will be at least one session of mental health services use (either online or in-person) assessed at 6 weeks, 6 months, and 2 years. Using hierarchical logistic regression, we will also examine efficacy in reducing or preventing number of students with mental health disorders (i.e., a positive screen for at least one of anxiety, depression, or ED as the outcome reflecting a "clinical case") assessed at 6 weeks, 6 months and 2 years, with a primary endpoint of 2 years. This allows for a single, universal outcome applicable to everyone in the study. Both logistic regression models will include random intercepts for colleges and for students nested within colleges, and account for repeated assessments within students, and will estimate the following fixed effects: main effect of time (coded as a factor variable, including baseline, 6-weeks, 6-months, and 2 years), treatment condition, and two-way interaction between time and treatment condition.

To evaluate reduction in disorder-specific symptoms (Aim 2b) and improvement in quality of life (Aim 2c), multilevel models will be used. Analyses of symptom change will be conducted within each clinical disorder subgroup separately with relevant symptoms as the response variables. We will also use a z-score to standardize primary symptom measures to obtain an estimate for a unified intervention effect. All symptom models will include random intercepts for colleges and for students nested within colleges, account for repeated assessments within students, and will estimate the following fixed effects: main effect of time, treatment condition, and two-way interaction between time and treatment condition. Parameter estimates from these models will allow separately

---

comparing change between arms from pre to 6 weeks, pre to 6 months, and from pre to 2-year follow-up. Each model will use dummy-coded factor terms as a stringent test of the treatment to ensure that: 1) treatment was associated with significantly greater change from pre to post than the control group; and 2) gains made in treatment at 6 weeks are maintained and significantly greater than baseline at each follow-up.

Analyses for Aim 3 (targets, other mediators, within-mobile program predictors, moderators). Potential mediators are categorized into three groups: 1) clinical targets (Aim 3a and Aim 3b); 2) early engagement with services (Aim 3c); and 3) early clinical response/rapid response (Aim 3c). We will test for mediation using structural equation models (SEM) with confidence intervals derived from bootstrapping of indirect effects and total effects. We will examine targets and mediators preceding changes in outcomes. To draw more informative and coherent conclusions across the three disorders, we will explore meaningful transdiagnostic clinical targets as well as disorder specific targets. For transdiagnostic mediator outcomes, binary clinical case status and quality of life measures are natural outcome measures, but for symptom outcomes, we will use standardized symptom scores (for transdiagnostic outcomes) and nonstandardized symptoms scores (for disorder-specific outcomes). Moderated mediation (with treatment vs control as the moderator) will be tested by constraining the indirect effect to be equal across treatment and control groups and testing differences in chi-square fit. Any significant misfit caused by specifying the indirect effect of each mediator to be equal suggests that there are significant differences in this mediational path between the treatment and control. All mediational paths between the primary predictor and outcome will be estimated simultaneously to account for any and all interdependence between paths and to ensure these interdependencies do not bias estimation. Note that in applying moderated mediation analyses to both transdiagnostic and disorder-specific targets, we will be simultaneously testing whether the intervention engages the targets (Aim 3a) and whether intervention-induced changes in targets are associated with clinical benefit (Aim 3b). Putative moderators (Aim 3e) will examine interaction terms with time point and random assignment in regressions to identify subgroups that benefit most from treatment, and others for whom additional tailoring may be necessary in future refinements of the delivery model. In cases where moderators are significant, we will then conduct mediator analyses separately by subgroups defined by these moderators, because different intervention effects often imply different mechanisms by which effects are occurring. In moderation models, results will estimate the following fixed effects: 1) main effect of time, treatment condition, and each proposed moderator; 2) two-way interactions between time and treatment condition, treatment condition and each moderator, and time and each moderator; and 3) three way interactions between time, treatment condition, and each moderator. The models will also estimate random effects of time nested within individuals, and intercepts nested within campuses. Within-mobile treatment predictors of change (Aim 3d) will use multilevel models using the fixed effects of maineffects of time, and each within-mobile program predictor, and the interaction between within-mobile program predictors and time estimating random effect of time nested within individuals and intercepts nested within campuses.

Analyses for Aim 4: Economic evaluation analyses (Aim 4a) were designed to provide information for stakeholders considering implementing the mobile platform^217. As such, analyses will be conducted from the payer's perspective to reflect opportunity cost for the payer. We will use TreeAge software, taking a multistep approach. Overall, the model will be evidence-based and fully validated using study data. A decision analytic

---

model using a microsimulation approach will be used to provide the most flexibility for testing model assumptions and provide clear evidence to decision-makers concerning reliability of results. Internal validation of the model will be conducted by comparing outcomes of participants whose data were used to construct the model to their predicted outcomes. Model fit will be tested using the R^2 statistic for continuous data and the chi-squared statistic for categorical data. External validity will be tested by comparing the model's predicted outcome to actual for participants who were "excluded" from the model-building process. The outcome of interest is the net benefit of the intervention compared to usual care at 2 years. Sensitivity of the decision model to the assumptions, including time frame, discount rate, and perspective, will be thoroughly tested using deterministic and probabilistic sensitivity analyses. We will also calculate incremental cost-effectiveness ratios, corresponding to the incremental difference (intervention vs. control) in costs divided by the incremental difference in the primary outcome, the number of clinical cases at 2-year follow-up. Monte Carlo simulations and cost-effectiveness acceptability curves will be used to present uncertainty around this estimate. Academic outcomes (Aim 4b) will be analyzed using the methods described for the primary outcomes under Aim 1. Academic outcomes will also be included into cost analyses, by translating drop-outs from college into losses in tuition (for institutions) and losses in lifetime expected productivity. Stakeholder attitudes (Aim 4c) will be assessed for variation using descriptive statistics, and will be used to predict intention to adopt the platform using ordered probit regressions (with Likert categorical variables corresponding to intention to adopt).

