(excluding anorexia nervosa, for which more intensive medical monitoring is warranted), which account for a substantial proportion of the mental health burden on college campuses, and who are not currently engaged in mental health services (N=7,884; of 146,000 initially screened) will be randomly assigned to: 1) intervention via the mobile mental health platform; or 2) referral to usual care (i.e., campus health or counseling center). Our comprehensive mental health care platform can yield clinical benefit to students, appeal to university stakeholders, minimize barriers to implementation sustainability on campuses, and produce an economic return on investment compared to usual care. This population-level approach to service engagement has the potential to improve mental health outcomes for the 20+ million students enrolled in U.S. colleges and universities.

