### Full study inclusion criteria:

- Students who screen has high risk or clinical/subclinical for anxiety, depression, and, EDs
- Students who are not currently in treatment, i.e., in the past month.
- Own a smartphone.

Students who endorse suicidal ideation in the baseline screening assessment will be given a referral to seek in-person care, however, we decided not to exclude students with suicidality, given that only 20-40% of college students with mental health problems receive treatment. As such, we deemed it insufficient to exclude such individuals from receiving the intervention and only providing an in-person referral, given the goal of this proposal to narrow the treatment gap for mental health problems among college students.

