## **F Statistical Plan**

### ***F1 Sample Size Determination and Power***

Sample size was based on achieving greater than 80% power to detect minimally meaningful differences in primary and secondary outcomes. We will include 20 colleges with approximately equal numbers of participants per campus, and approximately 3,154 high risk and 3,154 clinical participants with complete follow-up data. All power estimates were derived from Monte Carlo simulations (a gold standard in power estimation). For all analyses, power estimation is based on an effect size of .2 (i.e., for the primary

---

outcome, a differential change of .2 in the treatment vs. control group; for moderator analyses, effect size was .2 for each moderation effect; for mediator analyses, each pathway within the mediation was estimated at .2). We thus have power to detect smaller differences than we anticipate based on assumptions; this extra power is important, given that smaller differences would still be clinically meaningful at a population scale, particularly considering the modest cost of this online intervention. Power for all secondary outcomes was also estimated within the Monte Carlo simulation using all moderators within the same model; and all mediators within the same model targeting a .2 effect size, reflecting a conservative approach to power calculation and model estimation. Results of the Monte Carlo simulations suggested we had greater than 90% power to detect all primary outcomes and greater than 80% power to detect all secondary outcomes.

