#### ***F4 Missing Outcome Data***

All analyses will be intent-to-treat analyses, using full-information maximum likelihood to handle missing data.

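### The Aim 2a–2c models leave the baseline arm difference free; a shared baseline would sharpen the 2-year caseness interaction, with a smaller and conditional gain for continuous outcomes

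*Combined protocol and SAP*

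**What the plan says.** For caseness (Aim 2a), F3 specifies a hierarchical logistic model with a "main effect of time (coded as a factor variable, including baseline, 6-weeks, 6-months, and 2 years), treatment condition, and two-way interaction" between the two. One sentence sets the random effects for this model and for Aim 1 uptake together: "Both logistic regression models will include random intercepts for colleges and for students nested within colleges". The symptom models repeat the same fixed effects; quality of life (Aim 2c) is covered by implication. For these, "All symptom models will include random intercepts for colleges and for students nested within colleges", and the stated use of the estimates is "comparing change between arms from pre to 6 weeks, pre to 6 months, and from pre to 2-year follow-up". F3 also says that repeated assessments are accounted for, without giving a residual structure.

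F3 makes 2 years the primary caseness endpoint but does not say which 2-year contrast is tested. F1 describes its effect size as a difference between arms in change, which points to the interaction. The Aim 4a cost-effectiveness ratio uses the count of cases at 2 years, which reads as a level.

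On missing data, F4 says: "All analyses will be intent-to-treat analyses, using full-information maximum likelihood to handle missing data". No section constrains the baseline arm means to be equal or adds the baseline value as a covariate.

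**The concern.** With baseline as the reference occasion, the treatment main effect is the arm difference at baseline. By D1, 2.d and E1, students are randomised individually; caseness and symptoms come from the eligibility screen before randomisation, and quality of life from a survey completed before the arm is disclosed. The true baseline difference is therefore zero by design. Estimating it spends information, and its sampling error is carried into every difference in change.

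Precision is at stake, chiefly for the primary outcome. It has some value because F1 itself says that differences below .2 would still matter clinically at population scale.

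**Working it through.** **Inputs from the documents.** Randomised: "N=7,884; of 146,000 initially screened". Follow-up: "approximately 3,154 high risk and 3,154 clinical participants with complete follow-up data", so 6,308 in total, and 6,308/7,884 = 0.80.

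**Assumptions, not in the documents.** 1:1 allocation (3,942 per arm randomised, 3,154 with 2-year data); two-sided alpha 0.05; rho, the baseline to 2-year correlation; k, baseline SD divided by 2-year SD; and the student random-intercept variance.

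**1. The plan's own power.** F1 gives only bounds (above 90% primary, above 80% secondary) and no correlation, base rate or scale for .2, so no point value can be reproduced. The bounds are credible at .2 SD. Even for change scores with rho = 0 and k = 1, SE = √(4/3,154) = 0.0356, and power = Φ(0.2/0.0356 − 1.96), above 99.9%.

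**2. Continuous outcomes.** In 2-year SD units, with n0 and n2 per arm at baseline and 2 years:
- planned change contrast: variance = 2[(1−rho²)/n2 + (rho−k)²/n0]
- shared baseline, unstructured covariance: variance = 2(1−rho²)/n2

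Information lost is 1 minus the ratio of the second to the first. The lower figure uses all randomised (n0 = 3,942; 2-year data missing at random, interim visits of non-completers ignored), the higher one completers only (n0 = 3,154).

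| k | rho 0.2 | rho 0.5 | rho 0.8 |
|---|---|---|---|
| 1 | 35–40% | 21–25% | 8–10% |
| 0.8 | 23–27% | 9–11% | 0% |

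At k = 0.6 the loss is 12–14% at rho 0.2, 7–9% at 0.3 and 1% at 0.5. It is nil whenever k = rho. The smallest effect with 80% power (2.80 × SE, completers) is, at k = 1 and rho 0.2, 2.80√(3.2/3,154) = 0.089 SD planned against 2.80√(1.92/3,154) = 0.069 SD shared. At k = 0.6 and rho 0.5 it is 0.062 against 0.061.

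**3. Clinical-disorder subgroups.** Selection on the baseline score narrows its spread. As an illustration, take a normal score with the top 8% or 15% selected (Table 3 projects 15% for clinical depression and 8% for clinical generalized anxiety and eating disorder) and an unselected correlation R of 0.3–0.7. The selected baseline variance is v = 1 − λ(λ−c), where c is the cut-off and λ the normal density at c divided by the fraction selected. This gives v = 0.158 at 8% and 0.195 at 15%. Then k = √[v/(R²v + 1 − R²)], which is 0.41–0.57, and rho = R·k. Put into step 2 for completers, the loss is 2.7–9.5%.

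**4. Random intercepts alone.** If the constraint is fitted with only a student random intercept while the true baseline SD differs from the follow-up SD, the weights are wrong. With follow-up SDs of 1, all correlations equal to rho and complete data, the constrained estimate has variance about 5% higher than the planned contrast at k = 0.6, rho 0.5 and about 8% higher at k = 0.8, rho 0.8. With unstructured covariance the same cases give a 1% gain and no change.

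**5. Caseness.** Expected information of the four-occasion logistic model with a student random intercept (numerical quadrature). The college intercept is omitted because randomisation is within college. Baseline cases are 50% (F1's equal split), control cases at 2 years 45% (assumed), log odds ratio −0.2. SEs are for the 2-year effect.

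| Student variance | Interaction, completers | Interaction, all randomised | Shared baseline | Loss, completers | Loss, all randomised |
|---|---|---|---|---|---|
| 0.5 | .0756 | .0721 | .0563 | 44% | 39% |
| 1 | .0788 | .0755 | .0605 | 41% | 36% |
| 4 | .0920 | .0892 | .0769 | 30% | 26% |
| 8 | .1034 | .1009 | .0902 | 24% | 20% |

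For the 2-year level contrast the loss runs from 1% at variance 0.5 to 22% (all randomised) or 26% (completers) at variance 8. With 35% control cases at 2 years the interaction loss is 37% down to 19% (all randomised) or 42% down to 23% (completers).

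**The case against.** The planned model is valid, its contrast is stated openly, and F3 presents the dummy-coded form as a deliberately stringent test. On that view a constrained model is only a preference. It is true that nothing here is biased, and a reader who inferred bias or an underpowered trial would go beyond the documents: power at .2 SD exceeds 99.9% either way. Power for the caseness interaction would look short only if .2 were a log odds ratio (all randomised, student variance 1: 75% planned, 91% shared), and F1 does not say that it is. For the caseness interaction, though, the efficiency loss holds across the whole assumed range, so the preference argument does not dispose of it.

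Three limits stand.
- A reader might infer that the disorder-specific models, having fewer students, gain most. Selection makes the opposite likely, and the documents give no untreated subgroup sizes, so no subgroup power can be claimed.
- A reader might infer that dropping the term always helps. Under random intercepts alone it can cost precision. F3 leaves the residual structure open, so it cannot be assumed to be intercept-only either.
- The caseness figures need a clinical case to exclude high-risk students. F1 and Table 3 separate the two groups, which supports that reading. If high-risk students counted as cases, everyone would be a case at baseline: the free term could not be estimated and baseline caseness would add no precision.

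**Conclusion.** The concern holds as an efficiency improvement available at no data cost. Its main value is for the primary outcome: about 20–44% of the information on the 2-year caseness interaction, or 1–26% if the effect is the level contrast. This rests on the assumed student variances, 1:1 allocation, about half the students being cases at baseline, and 45% control cases at 2 years. For quality of life, which is not used for selection, k near 1 is plausible and the loss could reach 35–40% at low correlation. In the clinical-disorder symptom models it is probably single-digit. Naming the caseness contrast settles what is tested but adds no precision by itself; with a shared baseline, the interaction and the level contrast become the same parameter.

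**What to change.** For Aims 2a–2c:
- Keep baseline in the outcome vector, drop the treatment main effect so that both arms share one baseline level, and keep time and the treatment-by-follow-up terms.
- Name the 2-year time-by-treatment term as the primary caseness effect, and state that a clinical case means clinical, not high-risk, status.
- For continuous outcomes, pair the constraint with an unstructured within-student covariance, or use the baseline score as a covariate instead. For caseness, a baseline covariate in the logistic model targets a different conditional odds ratio and is not interchangeable.
- Keep the planned change contrasts as a sensitivity analysis.

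Split the sentence that specifies both logistic models, so that the change does not spill over to Aim 1. Uptake is assessed only after baseline, and entrants are "Students who are not currently in treatment, i.e., in the past month", so it needs its own specification. Check that Aim 4b, which borrows the Aim 1 method, still points to the right text. Leave the exploratory moderation models out of the change, and say whether they keep their free baseline terms.

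The cost is SAP wording only, with no new data.

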## **C Study Objectives**

### ***C1 Study Aims***

Our study aims are as follows:

- 1) Aim 1: Examine uptake (i.e., individuals beginning treatment) of the mobile mental health platform compared to referral to usual care.
- 2) Aim 2: Evaluate the effectiveness of the mobile mental health platform, compared to usual care, in (2a) reducing the number of individuals with mental health disorders (primary outcome); (2b) reducing disorder-specific symptoms (secondary outcome); and (2c) improving quality of life and functioning (secondary outcome).
- 3) Aim 3: (3a) Examine if the mobile intervention changes targets previously found to be associated with outcomes, both transdiagnostic (i.e., decreased dysfunctional cognitions, increased use of CBT skills) and disorder-specific (i.e., reduced avoidance for anxiety, increased behavioral activation for depression, reduced dietary restraint and weight/shape concerns for EDs); (3b) determine if changes in targets are associated with clinical benefit; and (3c; exploratory) identify other putative mediators of change (e.g., early engagement in help services, rapid response), (3d; exploratory) within-mobile program predictors of outcome (e.g., sessions completed), and (3e; exploratory) treatment moderators.
- 4) Aim 4 Evaluate stakeholder-relevant outcomes: (4a) costeffectiveness; (4b) students' academic performance; and (4c) attitudes.

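### The equality test on indirect effects across arms does not isolate whether the intervention changes the targets (Aim 3a), although the plan says it tests Aims 3a and 3b together

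*Combined protocol and SAP*

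**What the plan says.** Section C1 poses two mechanism questions and keeps the exploratory label for 3c to 3e. Aim 3a is to "Examine if the mobile intervention changes targets previously found to be associated with outcomes". Aim 3b is to "determine if changes in targets are associated with clinical benefit".

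Section F3 describes two steps for these aims:

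- **Mediation.** The plan will use "structural equation models (SEM) with confidence intervals derived from bootstrapping of indirect effects and total effects". It adds that "All mediational paths between the primary predictor and outcome will be estimated simultaneously". That predictor is not identified anywhere.
- **Moderated mediation.** "Moderated mediation (with treatment vs control as the moderator") is tested by "constraining the indirect effect to be equal across treatment and control groups and testing differences in chi-square fit". Misfit under the constraint "suggests that there are significant differences in this mediational path between the treatment and control".

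F3 then states that, by applying the moderated mediation analyses to transdiagnostic and disorder-specific targets, "we will be simultaneously testing whether the intervention engages the targets (Aim 3a") together with Aim 3b. No model in F3 is stated with a target as its response. The arm-by-time models described there are for uptake, case status, symptoms and quality of life.

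**The concern.** Aim 3a asks about the effect of random assignment on a target, which is a single path. In a two-group model arm defines the groups, so it has no variance within either group and cannot start a path there. The equality constraint acts on the product of two within-arm paths: predictor to target (a) and target to outcome (b). A difference between the products can come from a, from b, or from both. Equal products do not mean equal a.

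As worded, misfit would be read as the intervention engaging its targets and good fit as failure to engage them. Either reading could be wrong. At stake is the trial's mechanism claim: whether the program changes avoidance, behavioral activation, dietary restraint, weight and shape concerns, dysfunctional cognitions and use of CBT skills.

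**Working it through.** **Inputs from the documents.** F1 gives about 3,154 high-risk and 3,154 clinical participants with complete follow-up, 6,308 in all, and an effect of .2 for each mediation pathway. E2 schedules the targets at baseline and 6 weeks.

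**Assumptions, not in the documents.** Two-sided 5% level, 1:1 allocation, unit residual variances, no college clustering, continuous outcome, and the path values below. The figure of 1,577 per arm is half of one 3,154 stratum. Transdiagnostic targets could use 3,154 per arm.

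**The plan's own figure.** F1 states more than 80% power for secondary outcomes. Joint significance of an arm-to-target effect of .2 SD and a target-outcome slope of .2 has power above 99.9% at N = 6,308. This agrees with the stated bound, but it is not a reproduction, because the simulation inputs are not given.

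**Method.** Two thousand simulated trials per setting. A one-degree-of-freedom Wald test of a_T·b_T = a_C·b_C stands in for the chi-square difference test, to which it is asymptotically equivalent. It is compared with a direct test of the arm difference on the target. Simulation error near 5% is about √(.05 × .95 / 2,000) = 0.5 percentage points.

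**Reading 1: the predictor is time.** Here a is the mean target change within an arm, and b is the slope of outcome change on target change. The variance of the estimated product is about (a² + b²)/n.

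| Setting (T vs C), 1,577 per arm | Equality test rejects | Direct arm contrast rejects |
|---|---|---|
| a .2 vs .2, b .4 vs .2 | 86.1% | 4.4% |
| a .4 vs .2, b .2 vs .2 | 85.8% | 100% |
| a .4 vs .2, b 0 vs 0 | 4.9% | 100% |
| a .4 vs .2, b .2 vs .4 | 4.4% | 100% |

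Hand check of the first row:
- Product difference: .2 × .4 − .2 × .2 = .04.
- Standard error: √[(.04 + .16 + .04 + .04)/1,577] = √(.28/1,577) = .0133.
- z = .04/.0133 = 3.0, so power is about Φ(3.0 − 1.96) = 85%.

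The second row gives the same difference (.08 − .04 = .04) and the same variance sum (.16 + .04 + .04 + .04 = .28). Its power is therefore the same. The test responds identically to a difference in engagement and to a difference in slope alone.

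Hand check of the direct contrast for .4 vs .2: z = .2/√(2/1,577) = 5.6, so power is above 99.9%.

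At 3,154 per arm the first three equality-test rows become 99.2%, 98.8% and 5.6%. At 500 per arm they become 38.7%, 37.6% and 4.3%.

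**Reading 2: the predictor is a baseline variable.** An arm effect on the target then falls in the target's intercept, which the constraint does not touch. With a = .5 and b = .2 in both arms and a .2 SD arm shift in the target, the equality test rejects 4.7% of the time and the direct contrast 100% (1,577 per arm). With no shift but b = .3 vs .1, the equality test rejects 99.8%.

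**The case against.** The strongest reply is that F3 plans an SEM with bootstrapped indirect effects before the equality test. In a two-arm trial, treatment is a natural candidate for the unnamed primary predictor. On that reading the SEM contains an arm-to-target path, and a non-zero indirect effect would require both paths to be non-zero. This stands in part: a reader who inferred that the plan contains no arm-to-target path at all would be going beyond the text. But the plan does not name the predictor or say that the arm-to-target path will be reported, and it credits the joint answer to the moderated mediation step. A null indirect effect would still leave Aim 3a open, since the target may have moved while the slope was near zero.

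A second reply is that the test is not blind to engagement. That is right: with time as predictor and equal non-zero slopes it rejects about 86% of the time for target change of .4 against .2. The fault is lack of specificity.

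A third is that the path values are chosen, and that the matched-product row gives about 5% by construction. That is also fair. The rows show what the test can do, not how likely each situation is.

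**Conclusion.** The point holds as a defect of the stated rule: the product-equality test does not isolate Aim 3a, so its result could mislead in either direction. The algebra does not depend on the assumed values. The sizes (about 86% rejection with identical engagement, about 5% with clear engagement and zero slopes) do depend on them, and on 1,577 per arm, 1:1 allocation, no clustering and time as predictor.

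Three stronger inferences are not supported:

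- **That Aim 3a will be answered wrongly.** It could be. When slopes are non-zero and similar across arms, rejection would point the right way.
- **That the mediation power statement in F1 is false.** If every path is .2 in both arms, the products are equal and the equality test is under its null (4.3% rejection at 1,577 per arm). But F1 may mean an arm-to-target path of .2, which is well powered. The text does not say which model was simulated.
- **That the main results are affected.** The models for uptake, case status, symptoms and quality of life do not rely on this test.

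**What to change.** Amend the Aim 3 text in F3 as follows:

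1. **Aim 3a.** Test the arm effect on each 6-week target, adjusted for its baseline value, with a random intercept for college as in the other F3 models.
2. **Aim 3b.** Name arm as the predictor in the SEM, running from arm to 6-week target to 6-month and 2-year outcome, adjusted for baseline target and baseline outcome. Report the arm-to-target path, the target-outcome path and the bootstrapped indirect effect.
3. **Multi-group model.** Keep it only to ask whether the target-outcome path differs by arm, and place the equality constraint on that path rather than on the product.
4. **Wording.** Delete the statement that the moderated mediation analyses answer Aims 3a and 3b together.

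The cost is SAP wording. The targets are already collected at baseline and 6 weeks, and no new software is needed. Under the assumptions above, a .2 SD arm contrast has more than 99.9% power at 1,577 per arm and 88.5% at 500 per arm.
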